**Table 22. Combination A: Operating Characteristics**

Scenarios	Participant allocation (%)			Pr (declare MTD) (%)			% stop (no MTD)	Average sample size
	TT	OD	UD	TT	OD	UD		
Prior means	100	0	0	92.1	0	0	8.0	8.5
With under dose and overdose	81.1	18.9	0	92.1	0	0	8.0	8.5

**Table 22. Combination A: Operating Characteristics**

Scenarios	Participant allocation (%)			Pr (declare MTD) (%)			% stop (no MTD)	Average sample size
	TT	OD	UD	TT	OD	UD		
With under dose and target dose	64.0	0	35.9	96.1	0	0	3.9	8.8

### **13. APPENDIX B: SUB-STUDY B: SASANLIMAB + AXITINIB + SEA-TGT**

#### **13.1. Schedule of Activities (SoA): Sub-Study B**

The [SoA](#) table provides an overview of the sub-study visits and procedures. Refer to [Section 8](#) of the master protocol and [Section 13.8](#) of this sub-study appendix for detailed information on each procedure and assessment required for compliance with the protocol.

The investigator may schedule unplanned visits in addition to those listed in the [SoA](#) table, in order to conduct evaluations or assessments required to protect the well-being of the participant, or if otherwise clinically indicated.

**Table 23. Schedule of Activities Sub-Study B Phase 1b & Phase 2**

Visit Identifier a	Pre-Screening b	Screening b (≤28 days prior to first dose)	Treatment Period									Follow-Up d			
			Cycle 1 (Days 1 to 21)		Cycle 2 (Days 1 to 21)		Cycles 3 & 4 (Days 1 to 21)	Cycle 5 (Days 1 to 21)		Cycles ≥ 6 (Days 1 to 21)		EOT c	Day 30 d	Days 60, 90, & 180 d	Survival d
			Day 1	Day 8	Day 1	Day 8	Day 1	Day 1	Day 8	Day 1	Day 1				
Visit Window				±1	±2	±2	±2	±2	±2	±2		±7	±7	±7	
Informed consent e	X	X													
Eligibility review	X	X	X												
Tumor and medical history f		X													
Substance and tobacco use		X								X					
Physical examination g		X	X	X	X		X	X	X	X	X				
Height		X													
Weight		X	X		X		X	X		X	X				
In-clinic Vital signs h		X	X	X	X		X	X	X	X	X	X			
Home Blood Pressure Monitoring i			(continuous starting C1D1)												
ECHO/MUGA j		X									X				
ECOG performance status k		X	X												
Triplicate 12-lead ECG l			X												
Single 12-lead ECG l		X		X	X		X	X		X	X	X			
Laboratory Assessments of Hematology and Blood Chemistry m		X	X	X	X	X	X	X	X	X	X	X			
Coagulation m		X	X		X		X	X		X	X	X			
Urinalysis n		X	X	X	X	X	X	X	X	X	X	X			
Pregnancy test o		X	X		X		X	X		X	X	X	X		
Hepatitis B, C tests p		X													
Endocrinology tests m		X	Every 4 cycles starting at C4D1												
Allocation to study intervention q			X												
Dispensing of axitinib			X		X		X	X		X					

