### 2.2.2. Clinical Overview

Sasanlimab is being evaluated as a single-agent in Study B8011001 (146 participants with locally advanced or metastatic melanoma, squamous cell carcinoma of the head and neck, ovarian cancer, sarcoma, NSCLC, UC, or other solid tumors); as a single-agent in Study B8011007 (8 participants with advanced malignancies); and in combination with BCG in Study B8011006 (20 participants with high risk non muscle invasive bladder cancer).

Anti-tumor activity of single-agent sasanlimab has been demonstrated in Study B8011001. As of the data cutoff of 01 November 2019, efficacy has been evaluated in 67 participants with NSCLC and 38 participants with UC who were administered sasanlimab 300 mg SC Q4W. The ORR (95% Exact CI) was 20.9% (11.9%-32.6%) in the NSCLC cohort and 21.1% (9.6%-37.3%) in the UC cohort. Median (range) duration of partial response was 230 days (57-445 days) in the NSCLC cohort and 183 days (23-371 days) in the UC cohort.

A total of 60 of 106 participants who were administered sasanlimab 300 mg SC experienced at least 1 treatment-related AE. Most commonly (>5%) reported treatment-related AEs were hyperthyroidism (10.4%), pruritus (7.5%), lipase increased (6.6%), and ALT increased, AST increased, amylase increased, hypothyroidism, rash, and anemia (5.7% each).

Sixteen (15.1%) participants reported  $\geq$  Grade 3 treatment related AEs. Grade 3 treatment-related AEs included lipase increased, amylase increased, and blood alkaline phosphatase increased (1.9% each); decreased appetite, hypermagnesemia, pneumonitis, ageusia, anosmia, jaundice, blood potassium increased, transaminases increased, lymphocyte count decreased, asthenia, fatigue, cognitive disorder, and hypotension (0.9% each). Grade 4 treatment-related AEs included lipase increased, neutrophil count decreased, and white blood cell count decreased (0.9% each). Grade 5 treatment-related AE included arrhythmia (n = 1, 0.9%).

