 ESC guidelines website: <https://www.escardio.org/Guidelines/Clinical-Practice-Guidelines>  
 AHA guidelines website: <http://professional.heart.org/professional/GuidelinesStatements/searchresults.jsp?q=&y=&t=1001>

Endocrine irAEs		
Endocrine Disorder	Initial Management	Follow-up Management
Grade 1 or Grade 2 endocrinopathies (hypothyroidism, hyperthyroidism, adrenal insufficiency, type I diabetes mellitus)	
 
-Continue study treatment
 
-Endocrinology consult if needed
 
-Start thyroid hormone replacement therapy (for hypothyroidism), anti-thyroid treatment (for hyperthyroidism), corticosteroids (for adrenal insufficiency) or insulin (for Type I diabetes mellitus) as appropriate
 
-Rule-out secondary endocrinopathies (ie, hypopituitarism / hypophysitis)
 
	
 
-Continue hormone replacement/suppression and monitoring of endocrine function as appropriate.
 

Grade 3 or Grade 4 endocrinopathies (hypothyroidism, hyperthyroidism, adrenal insufficiency, type I diabetes mellitus)	
 
-Withhold study treatment
 
-Consider hospitalization
 
- Endocrinology consult
 
-Start thyroid hormone replacement therapy (for hypothyroidism), anti-thyroid treatment (for hyperthyroidism), corticosteroids (for adrenal insufficiency) or insulin (for type I diabetes mellitus) as appropriate
 
-Rule-out secondary endocrinopathies (ie, hypopituitarism / hypophysitis)
 
	
 
-Resume study treatment once symptoms and/or laboratory tests improve to Grade <math>\leq</math> 1 (with or without hormone replacement/suppression).
 
-Continue hormone replacement/suppression and monitoring of endocrine function as appropriate.
 

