Hypopituitarism/ Hypophysitis (secondary endocrinopathies)	
 
-If secondary thyroid and/or adrenal insufficiency is confirmed (ie, subnormal serum FT4 with inappropriately low TSH and/or low serum cortisol with inappropriately low ACTH):               
 
-Refer to endocrinologist for dynamic testing as indicated and measurement of other hormones (FSH, LH, GH/IGF-1, PRL, testosterone in men, estrogens in women)
 
-Hormone replacement/suppressive therapy as appropriate
 
-Perform pituitary MRI and visual field examination as indicated
 
 
 
-If hypophysitis is confirmed: 
 
-Continue study treatment if mild symptoms with normal MRI. Repeat the MRI in 1 month
 
 
 
	
 
-Resume study treatment once symptoms and hormone tests improve to Grade <math>\leq</math> 1 (with or without hormone replacement).
 
-In addition, for hypophysitis with abnormal MRI, resume study treatment only once shrinkage of the pituitary gland on MRI/CT scan is documented.
 
-Continue hormone replacement/suppression therapy as appropriate.
 

Endocrine irAEs		
Endocrine Disorder	Initial Management	Follow-up Management
	
-Withhold study treatment if moderate, severe or life-threatening symptoms of hypophysitis and/or abnormal MRI. Consider hospitalization. Initiate corticosteroids (1 to 2 mg/kg/day prednisone or equivalent) followed by corticosteroids taper during at least 1 month
 
-Add prophylactic antibiotics for opportunistic infections
	

Other irAEs* (not described above)		
Grade of other irAEs (NCI-CTCAE v5.0)	Initial Management	Follow-up Management
Grade 2 or Grade 3 clinical signs or symptoms suggestive of a potential irAE	-Withhold study treatment pending clinical investigation	-If irAE is ruled out, manage as appropriate according to the diagnosis and consider re-starting study treatment -If irAE is confirmed, treat as Grade 2 or 3 irAE.
Grade 2 irAE or first occurrence of Grade 3 irAE	-Withhold study treatment -1.0 to 2.0 mg/kg/day prednisone or equivalent -Add prophylactic antibiotics for opportunistic infections -Specialty consult as appropriate	-If improves to Grade $\leq$ 1: -Taper steroids over at least 1 month and resume study treatment following steroids taper.

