- i. **Home BP monitoring:** Participants will monitor their BP at least twice daily (before taking each dose of axitinib) and record the results in the diary. See [Section 13.8.2.1](#).
- j. **ECHO/MUGA:** The same modality used during screening is to be used for any subsequent assessments. Assessment will also be performed if a participant experiences an AE which may be related to cardiac dysfunction in the opinion of the investigator, or as otherwise clinically indicated. See [Section 13.8.2.2](#).
- k. **Eastern Cooperative Oncology Group (ECOG) Performance Status:** See [Section 8.2.6](#).
- l. **Triplicate and Single 12 Lead electrocardiogram (ECG):** When triplicate ECG is requested, 3 serial 12-lead ECGs will be conducted within approximately 5-10 minutes total time. Triplicate ECGs on C1D1 will be collected prior to administration of any study intervention. For remaining timepoints, single ECG will be collected prior to administration of study intervention. When coinciding with blood sample draws for PK, ECG assessment is to be performed prior to blood sample collection, such that the blood sample is collected at the nominal time.
- m. **Hematology, Blood Chemistry, Endocrinology, and Coagulation tests:** See [Sections 10.2](#) and [13.10.1](#) for lists of Laboratory Tests. Not necessary to repeat on C1D1 if performed within 7 days prior to C1D1 as part of Screening. Subsequent assessments must be performed within 72 hours prior to the scheduled visit. Hematology and chemistry assessments on C2D8 may be drawn at a lab local to the participant and do not require on-site visit. See [Section 10.2](#) for more details about clinical lab assessments.

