- The efficacy and safety of axitinib in combination with avelumab was also evaluated in the Javelin Medley VEGF study (B9991027, NCT03472560) that included 41 patients with advanced/metastatic NSCLC who had received at least 1 prior platinum-containing therapy and 20 patients with advanced/metastatic UC who were treatment naïve.
  - The most common (>10%) treatment related AEs in the NSCLC cohort were hypertension (39%), hypothyroidism (29%), decreased appetite (27%), diarrhea (22%), fatigue (22%), and hand-foot syndrome (15%); and in the UC cohort were asthenia (20%), decreased appetite (15%), fatigue (15%), and hypertension (15%).
  - Avelumab + axitinib showed antitumor activity in both cohorts, and tumor reduction was observed regardless of PD-L1 expression status. The confirmed ORR was 31.7% (95% CI: 18.1,48.1) in the NSCLC cohort and 10% (95% CI: 1.2,31.7) in the UC cohort (all partial responses). Median PFS was 5.5 months (95% CI: 2.5,7.0) in the NSCLC cohort and 2.3 months (95% CI: 1.8,5.6) in the UC cohort.
- The efficacy of axitinib in combination with pembrolizumab was investigated in the Keynote-426 study (NCT02853331) in 861 patients with untreated advanced RCC.
  - The most common adverse reactions ( $\geq 20\%$ ) in patients receiving axitinib and pembrolizumab were diarrhea, fatigue/asthenia, hypertension, hypothyroidism, decreased appetite, hepatotoxicity, palmar-plantar erythrodysesthesia, nausea, stomatitis/mucosal inflammation, dysphonia, rash, cough, and constipation. Serious adverse reactions occurred in 40% of patients receiving axitinib in combination with pembrolizumab and those that occurred in  $\geq 1\%$  of patients receiving axitinib in combination with pembrolizumab included hepatotoxicity (7%), diarrhea (4.2%), acute kidney injury (2.3%), dehydration (1%), and pneumonitis (1%). Fatal adverse reactions occurred in 3.3% of patients receiving axitinib in combination with pembrolizumab and included 3 cases of cardiac arrest, 2 cases of pulmonary embolism and 1 case each of cardiac failure, death due to unknown cause, myasthenia gravis, myocarditis, Fournier's gangrene, plasma cell myeloma, pleural effusion, pneumonitis, and respiratory failure.
  - There were statistically significant improvements in OS, PFS, and ORR in the axitinib + pembrolizumab group vs. the sunitinib group. OS at 1 year was

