#### **13.4.5. Dose Limiting Toxicity**

Refer to master protocol [Section 4.3.3](#) for the definition of DLT.

The DLT observation period is the first 21 days starting with the first dose of any study intervention in the combination.

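### After the Screening baseline, scheduled endocrine tests wait until C4D1 and are not marked at EOT or Day 30, so mild or asymptomatic endocrine events are under-ascertained

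*Protocol*

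**What the plan says.** The endocrinology rows of Table 5 (section 12.1) and Table 23 (section 13.1) are marked at Screening and then carry the text "Every 4 cycles starting at C4D1". The laboratory footnote to Table 23, which names endocrinology, adds "Not necessary to repeat on C1D1 if performed within 7 days prior to C1D1 as part of Screening". A baseline value is therefore planned. In both tables the hematology and chemistry row is marked at EOT and Day 30; the endocrinology row is not.

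Section 8.11 calls for laboratory work at the EOT visit unless it was done within the preceding week, but it refers to the sub-study schedule for which assessments are due. Table 4 (section 10.2) defines the endocrine panel as ACTH, TSH and free T4. Tables 11 and 29 add nothing to it.

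On expected toxicity, section 2.2.2 lists the commonest treatment-related events of sasanlimab, starting with hyperthyroidism at 10.4% and including hypothyroidism at 5.7%. Section 13.2.2.3.1 reports hypothyroidism in 29% of the NSCLC cohort given avelumab plus axitinib, and section 13.2.3 names it as a potential combined toxicity. Suspected immune-related events are adverse events of special interest (section 8.3.8). Changes in clinical laboratory parameters are a secondary endpoint in both sub-studies (Tables 6 and 24).

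Section 10.10 has endocrinopathies of every grade worked up with the step "Rule-out secondary endocrinopathies (ie, hypopituitarism / hypophysitis" and confirms secondary disease by "subnormal serum FT4 with inappropriately low TSH and/or low serum cortisol with inappropriately low ACTH".

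**The concern.** The protocol identifies thyroid disease as the leading sasanlimab-related toxicity. In Sub-Study B it adds a drug whose combination with a PD-L1 inhibitor gave hypothyroidism in more than a quarter of an NSCLC cohort. These events are often defined by a laboratory value, so how many are counted depends on when the value is measured.

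Under the schedule, anyone who stops before C4D1 has a baseline value and no scheduled value after it. Anyone who stops between tests has no scheduled value at the end of treatment. The safety summaries (section 9.4.3.2) nevertheless run to at least 30 days after the last dose or to the day before new anti-cancer treatment, and laboratory tests are reported by worst value (section 9.4.3.2.2). At stake is how complete the counts of mild or asymptomatic endocrine events are in those summaries.

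**Working it through.** **1. The protocol's own rates.** Section 2.2.2 gives a denominator of 106. The whole numbers of participants that match the printed percentages are 11/106 = 10.38% (printed 10.4%) and 6/106 = 5.66% (printed 5.7%). For avelumab plus axitinib in NSCLC, 12/41 = 29.3% (printed 29%). The rates are internally consistent.

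**2. Test days.** C4D1 falls on day 1 + 3 × cycle length, and tests recur every 4 cycles.

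| | Cycle | First post-baseline test | Next test (C8D1) | Interval |
|---|---|---|---|---|
| Sub-Study A | 28 days | 1 + 84 = day 85 | 1 + 196 = day 197 | 112 days (16 weeks) |
| Sub-Study B | 21 days | 1 + 63 = day 64 | 1 + 147 = day 148 | 84 days (12 weeks) |

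With no EOT mark, the last scheduled value can precede the end of treatment by almost 16 weeks in A or 12 weeks in B.

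**3. Participants with no scheduled post-baseline test, Sub-Study B Phase 2.** The protocol gives no time on treatment. I assume it is exponential, with PFS medians quoted in the protocol as a proxy:

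- Arm B3 (n = 20, pretreated): 4.0 months, the salvage chemotherapy figure in section 2.
- Arms B1 and B2 (n = 40, treatment-naïve): a range from 5.5 months (avelumab plus axitinib in NSCLC, section 13.2.2.3.1) to 8.8 months (pembrolizumab plus chemotherapy, section 2).

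The share off treatment before C4D1 is 1 − 0.5^(t/m), with t = 63/30.44 = 2.07 months:

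- m = 4.0: 30.1%; × 20 = 6.0
- m = 5.5: 23.0%; × 40 = 9.2
- m = 8.8: 15.0%; × 40 = 6.0

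Totals are 6.0 + 6.0 = 12.0 at the low end and 6.0 + 9.2 = 15.2 at the high end, so about 12 to 15 of 60, or 20% to 25%. I give no share for Sub-Study A, because these medians do not describe its BRAF-mutated population on targeted treatment.

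**4. Primary endpoints.** For Sub-Study B, "The DLT observation period is the first 21 days starting with the first dose of any study intervention in the combination", so no scheduled post-baseline endocrine test falls inside that window; day 85 is likewise outside the 28-day window in A. However, section 4.3.3 exempts Grade 3 endocrinopathies controlled with medical therapy from counting as DLTs. The Phase 2 primary endpoints are tumor responses. The effect is confined to the secondary safety and laboratory endpoints.

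**5. Cortisol.** The adrenal limb of the section 10.10 confirmation is "low serum cortisol with inappropriately low ACTH". Table 4 supplies ACTH but not cortisol, so a scheduled sample alone cannot complete that limb. The thyroid limb needs free T4 and TSH, and both are in the panel.

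**The case against.** The strongest reply is that other routes of detection stay open. Adverse events are actively elicited for at least 90 days after the last dose (section 8.3.1), unscheduled laboratory tests are allowed at any time (section 8.2.4), and examinations and vital signs recur through treatment. This stands. A reader might infer that the main toxicity goes unmeasured, or that no testing happens before C4D1. The documents support neither: a Screening baseline exists, and symptomatic events will still be recorded. What the other routes do not replace is a systematic laboratory check in people without symptoms.

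Second, section 8.11 might already require endocrine tests at EOT, and section 10.12.3.1 counts endocrinology among the safety laboratory evaluations. The row is also a merged text cell, so its layout should be confirmed against the formatted table. But section 8.11 defers to the schedule for content. Either the tests are due at EOT and the rows should show it, or they are not due and the gap is real. It says nothing about Day 30 or the period before C4D1.

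Third, the proxy is weak. Treatment beyond progression is permitted (section 7.1.1), which lowers the shares, while stopping for toxicity raises them. Arm B3 excludes those with confirmed progression at the first or second assessment of earlier therapy. Six-weekly scans put only one planned assessment before day 64, so real departures would not follow a smooth curve. The range is indicative only.

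Fourth, a reader might take section 10.10 and Table 4 as contradicting each other on cortisol. They do not: section 10.10 describes a confirmatory work-up and does not say that the sample must be a scheduled one. Nor does missing cortisol bear on thyroid events.

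**Conclusion.** The point holds as a gap in safety measurement. Mild or asymptomatic biochemical endocrine events will be under-ascertained in the secondary safety and laboratory summaries of both sub-studies. The documents give no reference rate from which to size the shortfall in events. The measurable part is the number of Sub-Study B Phase 2 participants without a scheduled post-baseline test: about 12 to 15 of 60, under exponential time on treatment and the PFS proxies above.

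A reader might reach about 18 of 60 by applying the 4.0-month median to everyone (30.1% × 60 = 18.1). That is not supported: 40 of the 60 are treatment-naïve and must have a life expectancy of at least 12 months (section 5.1), whereas the 4.0 months comes from salvage chemotherapy. Nor do the documents show that a dose decision or primary analysis would change. The cortisol question is minor and limited to adrenal and pituitary events.

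**What to change.** Reconcile the endocrinology rows of Tables 5 and 23 with section 8.11 by marking the existing Table 4 panel at EOT and Day 30, and at one Day 1 draw already scheduled before C4D1 (for example C2D1 or C3D1). Blood is already taken at these visits, so no visit or procedure is added. The cost is the extra assays and the follow-up of some incidental abnormal values.

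Separately, reconcile Table 4 with section 10.10: either add cortisol to the panel, or state that it is obtained as part of the work-up when adrenal or pituitary disease is suspected. Neither change alters a treatment rule.

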**Table 23. Schedule of Activities Sub-Study B Phase 1b & Phase 2**

Visit Identifier a	Pre-Screening b	Screening b (≤28 days prior to first dose)	Treatment Period									Follow-Up d		
			Cycle 1 (Days 1 to 21)		Cycle 2 (Days 1 to 21)		Cycles 3 & 4 (Days 1 to 21)		Cycle 5 (Days 1 to 21)		Cycles ≥ 6 (Days 1 to 21)			
			Day 1	Day 8	Day 1	Day 8	Day 1	Day 1	Day 8	Day 1	EOT c	Day 30 d	Days 60, 90, & 180 d	Survival d
Administration of study treatment sasanlimab f			X		X			X	X		X			
Administration of study treatment SEA-TGT s			X		X			X	X		X			
Administration of study treatment axitinib t			Continuous BID starting C1D1											
Local site injection tolerability assessment u			X		X			X	X		X			
Tumor assessment v		X	Every 6 wks (±7 days) from C1D1 for the first 12 months, then every 12 wks (±7 days) thereafter according to calendar, regardless of treatment delays and until progressive disease assessed by investigator using RECIST v1.1 or start of new anti-cancer therapy											
Nonserious and serious adverse events w		X	→	→	→	→	→	→	→	→	→	→	→	→
Prior and Concomitant medication/surgery/ radiation & non-drug supportive interventions x		X	X	X	X			X	X	X	X	X		
Survival & subsequent anti-cancer therapy											X	X	X	X
Contraception check y		X	X		X			X	X		X	X	X	
Remote visit						X							X	X
PK for sasanlimab z			X	X	X			X	X	X	X (C7, C10, C13, C16, then every 6 cycles)			

**Table 23. Schedule of Activities Sub-Study B Phase 1b & Phase 2**

Visit Identifier a	Pre-Screening b	Screening b (≤28 days prior to first dose)	Treatment Period									Follow-Up d		
			Cycle 1 (Days 1 to 21)		Cycle 2 (Days 1 to 21)		Cycles 3 & 4 (Days 1 to 21)		Cycle 5 (Days 1 to 21)		Cycles ≥ 6 (Days 1 to 21)			
			Day 1	Day 8	Day 1	Day 8	Day 1	Day 1	Day 8	Day 1	EOT c	Day 30 d	Days 60, 90, & 180 d	Survival d
PK for SEA-TGT aa			X	X	X		X	X	X	X (C7, C10, C13, C16, then every 6 cycles)				
PK for axitinib bb			X	X	X		X	X	X					
Baseline tumor biospecimen cc		X												
Biobanked biospecimen for genetics dd			X											
Blood for cell-free (cf) DNA analysis ee			X		X		X (C4 only)				X			
Blood for specified genetic research ff		X	X	X	X									
Blood for T-Cell Receptor (TCR) analysis ii		X	X	X	X									
Immunogenicity for sasanlimab jj			X		X		X	X		X (C7, C10, C13, C16 and then every 6 cycles)	X			
Immunogenicity for SEA-TGT kk			X		X		X	X		X (C7, C10, C13, C16 and then every 6 cycles)	X			

a. **Day** relative to start of study intervention (Day 1).

**Table 23. Schedule of Activities Sub-Study B Phase 1b & Phase 2**

Visit Identifier a	Pre-Screening b	Screening b (≤28 days prior to first dose)	Treatment Period									Follow-Up d			
			Cycle 1 (Days 1 to 21)		Cycle 2 (Days 1 to 21)		Cycles 3 & 4 (Days 1 to 21)		Cycle 5 (Days 1 to 21)		Cycles ≥ 6 (Days 1 to 21)				
			Day 1	Day 8	Day 1	Day 8	Day 1	Day 1	Day 8	Day 1	EOT c	Day 30 d	Days 60, 90, & 180 d	Survival d	

- b. The **Pre-Screening** period is optional and allows local PD-L1 and genetic testing to start after completion of the pre-screening consent, and before the Screening period. **Screening:** To be performed within 28 days prior to first dose. Visit may be conducted over multiple days.
- c. **End of Treatment (EOT) Visit:** Conducted at the visit that the participant is discontinued from study treatment or no longer than 1 week after the decision to discontinue the participant from study treatment. See [Section 8.11](#).
- d. **Follow-up:** The initial safety follow-up visit will be conducted at the study clinic 30 days after the last dose of study intervention. The 60, 90, and 180-day follow-up may be conducted by remote contact (eg. telephone). See [Section 8.2.8](#). **Survival Follow-Up:** Only for Phase 2. Participants will be contacted every 12 weeks (±7 days) after the last clinic visit until death, lost-to-follow-up, study termination, end of study, or withdrawal of consent. See [Section 8.1.3](#).
- e. **Informed Consent:** Must be obtained prior to undergoing any study specific procedures. May be obtained more than 28 days prior to first dose.
- f. **Tumor History:** Includes history of disease under study including details of primary diagnosis, treatment history and staging. **Medical History:** Includes history other than the cancer under study. Abnormalities observed during screening are to be considered as medical history.
- g. **Physical examination (PE):** See [Section 8.2.1](#).
- h. **Vital Signs:** Includes temperature, blood pressure, and pulse rate. On Day 1 of each cycle, vital signs are to be measured within 60 minutes prior to administration of any study intervention (pre-dose), at the completion of the SEA-TGT infusion, and at the completion of the 2-hour-post-dose observation period (on Cycles 1, 2, 3 only).
- i. **Home BP monitoring:** Participants will monitor their BP at least twice daily (before taking each dose of axitinib) and record the results in the diary. See [Section 13.8.2.1](#).
- j. **ECHO/MUGA:** The same modality used during screening is to be used for any subsequent assessments. Assessment will also be performed if a participant experiences an AE which may be related to cardiac dysfunction in the opinion of the investigator, or as otherwise clinically indicated. See [Section 13.8.2.2](#).
- k. **Eastern Cooperative Oncology Group (ECOG) Performance Status:** See [Section 8.2.6](#).
- l. **Triplicate and Single 12 Lead electrocardiogram (ECG):** When triplicate ECG is requested, 3 serial 12-lead ECGs will be conducted within approximately 5-10 minutes total time. Triplicate ECGs on C1D1 will be collected prior to administration of any study intervention. For remaining timepoints, single ECG will be collected prior to administration of study intervention. When coinciding with blood sample draws for PK, ECG assessment is to be performed prior to blood sample collection, such that the blood sample is collected at the nominal time.
- m. **Hematology, Blood Chemistry, Endocrinology, and Coagulation tests:** See [Sections 10.2](#) and [13.10.1](#) for lists of Laboratory Tests. Not necessary to repeat on C1D1 if performed within 7 days prior to C1D1 as part of Screening. Subsequent assessments must be performed within 72 hours prior to the scheduled visit. Hematology and chemistry assessments on C2D8 may be drawn at a lab local to the participant and do not require on-site visit. See [Section 10.2](#) for more details about clinical lab assessments.

